#### 5.2.1.2 Dose Modification

Adverse events (both non-serious and serious) associated with pembrolizumab exposure may represent an immunologic etiology. These adverse events may occur shortly after the first dose or several months after the last dose of treatment. Pembrolizumab must be withheld for drug-related toxicities and severe or life-threatening AEs as per Table 3 below. See Section 5.6.1 for supportive care guidelines, including use of corticosteroids.

Table 3

Dose Modification Guidelines for Drug-Related Adverse Events

General instructions:

 
1. Corticosteroid taper should be initiated upon AE improving to Grade 1 or less and continue to taper over at least 4 weeks.
 
2. For situations where pembrolizumab has been withheld, pembrolizumab can be resumed after AE has been reduced to Grade 1 or 0 and corticosteroid has been tapered. Pembrolizumab should be permanently discontinued if AE does not resolve within 12 weeks of last dose or corticosteroids cannot be reduced to <math>\leq 10</math> mg prednisone or equivalent per day within 12 weeks.
 
3. For severe and life-threatening irAEs, IV corticosteroid should be initiated first followed by oral steroid. Other immunosuppressive treatment should be initiated if irAEs cannot be controlled by corticosteroids.
 

Immune-related AEs	Toxicity grade or conditions (CTCAEv4.0)	Action taken to pembrolizumab	irAE management with corticosteroid and/or other therapies	Monitor and follow-up
Pneumonitis	Grade 2	Withhold	
 
Administer corticosteroids (initial dose of 1-2 mg/kg prednisone or equivalent) followed by taper
 
	
 
Monitor participants for signs and symptoms of pneumonitis
 
Evaluate participants with suspected pneumonitis with radiographic imaging and initiate corticosteroid treatment
 
Add prophylactic antibiotics for opportunistic infections
 

	Grade 3 or 4, or recurrent Grade 2	Permanently discontinue		

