Diarrhea / Colitis	Grade 2 or 3	Withhold	
 
Administer corticosteroids (initial dose of 1-2 mg/kg prednisone or equivalent) followed by taper
 
	
 
Monitor participants for signs and symptoms of enterocolitis (ie, diarrhea, abdominal pain, blood or mucus in stool with or without fever) and of bowel perforation (ie, peritoneal signs and ileus).
 
Participants with <math>\geq</math> Grade 2 diarrhea suspecting colitis should consider GI consultation and performing endoscopy to rule out colitis.
 
Participants with diarrhea/colitis should be advised to drink liberal quantities of clear fluids. If sufficient oral fluid intake is not feasible, fluid and electrolytes should be substituted via IV infusion.
 

	Grade 4	Permanently discontinue		

AST / ALT elevation or Increased bilirubin	Grade 2	Withhold	
 
Administer corticosteroids (initial dose of 0.5- 1 mg/kg prednisone or equivalent) followed by taper
 
	
 
Monitor with liver function tests (consider weekly or more frequently until liver enzyme value returned to baseline or is stable)
 

	Grade 3 or 4	Permanently discontinue	
 
Administer corticosteroids (initial dose of 1-2 mg/kg prednisone or equivalent) followed by taper
 
	
Type 1 diabetes mellitus (T1DM) or Hyperglycemia	Newly onset T1DM or Grade 3 or 4 hyperglycemia associated with evidence of $\beta$ -cell failure	Withhold	
 
Initiate insulin replacement therapy for participants with T1DM
 
Administer anti-hyperglycemic in participants with hyperglycemia
 
	
 
Monitor participants for hyperglycemia or other signs and symptoms of diabetes.
 

Hypophysitis	Grade 2	Withhold	
 
Administer corticosteroids and initiate hormonal replacements as clinically indicated.
 
	
 
Monitor for signs and symptoms of hypophysitis (including hypopituitarism and adrenal insufficiency)
 

	Grade 3 or 4	Withhold or permanently discontinue 		

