## 5.4 Rescue Medications & Supportive Care

### 5.4.1 Supportive Care Guidelines

Subjects should receive appropriate supportive care measures as deemed necessary by the treating investigator. Suggested supportive care measures for the management of adverse events with potential immunologic etiology are outlined below. Where appropriate, these guidelines include the use of oral or intravenous treatment with corticosteroids as well as additional anti-inflammatory agents if symptoms do not improve with administration of corticosteroids. Note that several courses of steroid tapering may be necessary as symptoms may worsen when the steroid dose is decreased. For each disorder, attempts should be made to rule out other causes such as metastatic disease or bacterial or viral infection, which might require additional supportive care. The treatment guidelines are intended to be applied when the investigator determines the events to be related to pembrolizumab.

Note: if after the evaluation the event is determined not to be related, the investigator is instructed to follow the ECI reporting guidance but does not need to follow the treatment guidance. Refer to Section 5.2.1 for dose modification.

It may be necessary to perform conditional procedures such as bronchoscopy, endoscopy, or skin photography as part of evaluation of the event.

- **Pneumonitis:**
  - For **Grade 2 events**, treat with systemic corticosteroids. When symptoms improve to Grade 1 or less, steroid taper should be started and continued over no less than 4 weeks.
  - For **Grade 3-4 events**, immediately treat with intravenous steroids. Administer additional anti-inflammatory measures, as needed.

- Add prophylactic antibiotics for opportunistic infections in the case of prolonged steroid administration.
- **Diarrhea/Colitis:**  
Subjects should be carefully monitored for signs and symptoms of enterocolitis (such as diarrhea, abdominal pain, blood or mucus in stool, with or without fever) and of bowel perforation (such as peritoneal signs and ileus).
  - All subjects who experience diarrhea/colitis should be advised to drink liberal quantities of clear fluids. If sufficient oral fluid intake is not feasible, fluid and electrolytes should be substituted via IV infusion. For Grade 2 or higher diarrhea, consider GI consultation and endoscopy to confirm or rule out colitis.
  - For **Grade 2 diarrhea/colitis** that persists greater than 3 days, administer oral corticosteroids.

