  - For **Grade 3 or 4 diarrhea/colitis** that persists > 1 week, treat with intravenous steroids followed by high dose oral steroids.
  - When symptoms improve to Grade 1 or less, steroid taper should be started and continued over no less than 4 weeks.
- **Type 1 diabetes mellitus (if new onset, including diabetic ketoacidosis [DKA]) or ≥ Grade 3 Hyperglycemia, if associated with ketosis (ketonuria) or metabolic acidosis (DKA)**
  - For **T1DM or Grade 3-4 Hyperglycemia**
    - Insulin replacement therapy is recommended for Type I diabetes mellitus and for Grade 3-4 hyperglycemia associated with metabolic acidosis or ketonuria.
    - Evaluate patients with serum glucose and a metabolic panel, urine ketones, glycosylated hemoglobin, and C-peptide.
- **Hypophysitis:**
  - For **Grade 2** events, treat with corticosteroids. When symptoms improve to Grade 1 or less, steroid taper should be started and continued over no less than 4 weeks. Replacement of appropriate hormones may be required as the steroid dose is tapered.
  - For **Grade 3-4** events, treat with an initial dose of IV corticosteroids followed by oral corticosteroids. When symptoms improve to Grade 1 or less, steroid taper should be started and continued over no less than 4 weeks. Replacement of appropriate hormones may be required as the steroid dose is tapered.
- **Hyperthyroidism or Hypothyroidism:**  
Thyroid disorders can occur at any time during treatment. Monitor patients for changes in thyroid function (at the start of treatment, periodically during treatment, and as indicated based on clinical evaluation) and for clinical signs and symptoms of thyroid disorders.

- **Grade 2** hyperthyroidism events (and **Grade 2-4** hypothyroidism):
  - In hyperthyroidism, non-selective beta-blockers (e.g. propranolol) are suggested as initial therapy.
  - In hypothyroidism, thyroid hormone replacement therapy, with levothyroxine or liothyronine, is indicated per standard of care.
- **Grade 3-4** hyperthyroidism
  - Treat with an initial dose of IV corticosteroid followed by oral corticosteroids. When symptoms improve to Grade 1 or less, steroid taper should be started and continued over no less than 4 weeks. Replacement of appropriate hormones may be required as the steroid dose is tapered.
- **Hepatic:**
  - For **Grade 2** events, monitor liver function tests more frequently until returned to baseline values (consider weekly).
    - Treat with IV or oral corticosteroids

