### **7.2.5 Sponsor Responsibility for Reporting Adverse Events**

All Adverse events will be reported to regulatory authorities, IRB/IECs, in accordance with all applicable global laws and regulations

Table 6 Evaluating Adverse Events

An investigator who is a qualified physician, will evaluate all adverse events as to:

V4.0 CTCAE Grading	Grade 1	Mild; asymptomatic or mild symptoms; clinical or diagnostic observations only; intervention not indicated.
	Grade 2	Moderate; minimal, local or noninvasive intervention indicated; limiting age-appropriate instrumental ADL.
	Grade 3	Severe or medically significant but not immediately life-threatening; hospitalization or prolongation of hospitalization indicated; disabling; limiting self-care ADL.
	Grade 4	Life threatening consequences; urgent intervention indicated.
	Grade 5	Death related to AE
Seriousness	A serious adverse event is any adverse event occurring at any dose or during any use of Merck product that:	
	† Results in death ; or	
	† Is life threatening ; or places the subject, in the view of the investigator, at immediate risk of death from the event as it occurred (Note: This does not include an adverse event that, had it occurred in a more severe form, might have caused death.); or	
	† Results in a persistent or significant disability/incapacity (substantial disruption of one’s ability to conduct normal life functions); or	
	† Results in or prolongs an existing inpatient hospitalization (hospitalization is defined as an inpatient admission, regardless of length of stay, even if the hospitalization is a precautionary measure for continued observation. (Note: Hospitalization for an elective procedure to treat a pre-existing condition that has not worsened is not a serious adverse event. A pre-existing condition is a clinical condition that is diagnosed prior to the use of a pembrolizumab and is documented in the patient’s medical history.); or	
	† Is a congenital anomaly/birth defect (in offspring of subject taking the product regardless of time to diagnosis); or	
Is a new cancer ; (that is not a condition of the study) (although not serious per ICH definitions, is reportable to the Sponsor within 24 hours and to Merck within 2 working days to meet certain local requirements.); or		

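### Section 5.4.1 makes steroids for Grade 3-4 diarrhea/colitis wait more than a week, longer than for Grade 2 and with no counterpart in Table 3

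*Combined protocol and SAP*

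**What the plan says.** Steroid treatment of diarrhea/colitis is described in two places.

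- **Section 5.4.1 (Supportive Care Guidelines).** At Grade 2, the instruction covers an event "that persists greater than 3 days, administer oral corticosteroids". At the two higher grades, the corresponding instruction covers an event "that persists > 1 week, treat with intravenous steroids followed by high dose oral steroids". The section introduces its measures as suggestions. It says they apply once the investigator has judged the event related to pembrolizumab.
- **Section 5.2.1.2, Table 3.** The diarrhea/colitis row, on the Grade 2 or 3 line, says "Administer corticosteroids (initial dose of 1-2 mg/kg prednisone or equivalent) followed by taper". The management cell beside Grade 4 is blank in the text available, probably because a merged cell was lost. General instruction 3 at the head of the table says "For severe and life-threatening irAEs, IV corticosteroid should be initiated first followed by oral steroid".

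Section 5.2.1.2 sends the reader on with "See Section 5.6.1 for supportive care guidelines, including use of corticosteroids". Section 5.6.1 is about stopping treatment after a complete response. The supportive care text is in 5.4.1.

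**The concern.** A waiting time that lengthens with severity is the reverse of what one would expect, and the protocol gives no reason for it. Table 6 (Section 7.2.5) describes Grade 3 as "Severe or medically significant but not immediately life-threatening" and Grade 4 as "Life threatening consequences; urgent intervention indicated". Both Table 3 and Section 5.4.1 name bowel perforation as something to watch for in these patients.

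An investigator who follows 5.4.1 literally would hold back steroids for a week in severe or life-threatening colitis already attributed to the drug. One who follows Table 3 would not. At stake is the safety of individual patients, along with consistent management of a recognised toxicity. The efficacy inference is not touched.

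**Working it through.** The plan states no figure to reproduce here. The check is a comparison of texts, with one subtraction.

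**Step 1: the two sources side by side.**

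| Grade | Section 5.4.1: condition before steroids | Table 3: condition before steroids |
|---|---|---|
| 2 | lasts more than 3 days | none stated |
| 3 | lasts more than 1 week (7 days) | none stated in the colitis row or in general instruction 3 |
| 4 | lasts more than 1 week (7 days) | colitis cell blank; none stated in general instruction 3 |

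**Step 2: consistency within 5.4.1.** The Grade 3-4 threshold minus the Grade 2 threshold is 7 − 3 = 4 days. On day 5, for example, a patient with persistent Grade 2 diarrhea qualifies for oral steroids, while a patient with Grade 3 or 4 diarrhea of the same duration does not yet qualify for any.

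**Step 3: consistency with Table 3.** At Grade 3 the conflict is direct: an unconditional instruction in the colitis row against a wait of more than 7 days. At Grade 2 it is also direct, against a wait of more than 3 days. At Grade 4 it runs only through general instruction 3, because the row itself shows nothing for that grade.

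**Step 4: comparison with the other disorders in 5.4.1.** The section gives steroids for six immune-related disorders: pneumonitis, diarrhea/colitis, hypophysitis, hyperthyroidism, hepatic events, and renal failure or nephritis. (Infusion reactions and type 1 diabetes/hyperglycemia are not counted.) Only diarrhea/colitis carries a persistence condition, 1 of 6. For Grade 3-4 pneumonitis the instruction is to "immediately treat with intravenous steroids".

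**Step 5: is the week a diagnostic interval?** Section 5.4.1 asks for other causes to be excluded for every disorder, not only for colitis, and applies its treatment guidance after the event is judged drug-related. The text does not present the week as work-up time. A work-up rationale would also not explain a longer interval for the more severe grades.

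**Step 6: does any text settle the conflict?** Section 5.4.1 refers back to 5.2.1 only for dose modification. Section 5.2.1.2 refers forward for steroid use, but to the wrong section. Neither is said to take precedence.

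**The case against.** The best reply is that Table 3 gives a dose and a taper but no start time. On that reading Table 3 covers dose and drug action, while 5.4.1 supplies the timing, and the forward reference in 5.2.1.2 lends this some support. General instruction 3 can likewise be read as fixing the order of routes, intravenous before oral, and 5.4.1 keeps that order. The Grade 4 conflict is therefore indirect. The urgent-intervention wording in Table 6 is generic and does not name steroids.

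There are also real safeguards. Table 3 withholds pembrolizumab at Grade 2 or 3 and stops it permanently at Grade 4, with no persistence condition. Section 5.4.1 asks for monitoring, fluids, and consideration of gastroenterology consultation and endoscopy. It leaves care to the treating investigator, and Section 5.3.2 allows systemic glucocorticoids for suspected immune-related events. Nothing forbids earlier steroids.

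Much of this stands. Table 3 does not say steroids must start at onset, so the mismatch is between an unconditional and a conditional instruction. The safeguards make harm less likely. But even if 5.4.1 is taken as the sole source of timing, the longer wait for Grade 3-4 than for Grade 2 remains unexplained.

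**Conclusion.** The concern holds. Within 5.4.1 the Grade 3-4 threshold is 4 days longer than the Grade 2 threshold. Table 3 has no threshold at Grade 2 or 3, and its general instruction on severe and life-threatening events has none. The first statement rests on 5.4.1 alone. The second takes the absence of a condition in Table 3 to mean that none was intended. For Grade 4 it also relies on general instruction 3 applying to timing as well as route.

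The documents give no colitis incidence, so the number of patients affected among the approximately 25 planned cannot be stated. The correction should be made because the instruction concerns patient safety and is wrong as written. It has no bearing on the response-rate test, power or sample size.

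**What to change.** In one amendment:

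1. In Section 5.4.1, delete the one-week persistence condition so that Grade 3-4 diarrhea/colitis judged drug-related receives intravenous steroids without a waiting period.
2. Give Grade 2 one timing in both texts: either remove the 3-day condition from 5.4.1 or add it to Table 3.
3. State that Table 3 governs wherever it and 5.4.1 differ.
4. In Section 5.2.1.2, change the supportive care cross-reference from 5.6.1 to 5.4.1.

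The cost is wording only. No visit, sample size or analysis changes.

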## 5.5 Diet/Activity/Other Considerations

### 5.5.1 Diet

Subjects should maintain a normal diet unless modifications are required to manage an AE such as diarrhea, nausea or vomiting.

### 5.5.2 Contraception

Pembrolizumab may have adverse effects on a fetus in utero. Furthermore, it is not known if pembrolizumab has transient adverse effects on the composition of sperm. Non-pregnant, non-breast-feeding women may be enrolled if they are willing to use 2 methods of birth control or are considered highly unlikely to conceive. Highly unlikely to conceive is defined as 1) surgically sterilized, or 2) postmenopausal (a woman who is  $\geq 45$  years of age and has not had menses for greater than 1 year will be considered postmenopausal), or 3) not heterosexually active for the duration of the study. The two birth control methods can be either two barrier methods or a barrier method plus a hormonal method to prevent pregnancy. Subjects should start using birth control from study Visit 1 throughout the study period up to 120 days after the last dose of study therapy.

The following are considered adequate barrier methods of contraception: diaphragm, condom (by the partner), copper intrauterine device, sponge, or spermicide. Appropriate hormonal contraceptives will include any registered and marketed contraceptive agent that contains an estrogen and/or a progestational agent (including oral, subcutaneous, intrauterine, or intramuscular agents).

Subjects should be informed that taking the study medication may involve unknown risks to the fetus (unborn baby) if pregnancy were to occur during the study. In order to participate in the study they must adhere to the contraception requirement (described above) for the duration of the study and during the follow-up period defined in section 7.2.2-Reporting of Pregnancy and Lactation to UCLA DSMB. If there is any question that a subject will not reliably comply with the requirements for contraception, that subject should not be entered into the study.

### 5.5.3 Use in Pregnancy

If a subject inadvertently becomes pregnant while on treatment with pembrolizumab, the subject will immediately be removed from the study. The site will contact the subject at least monthly and document the subject's status until the pregnancy has been completed or terminated. The outcome of the pregnancy will be reported to the study site's Data Safety Monitoring Board without delay if the outcome is a serious adverse experience (e.g., death, abortion, congenital anomaly, or other disabling or life-threatening complication to the mother or newborn).

The study investigator will make every effort to obtain permission to follow the outcome of the pregnancy and report the condition of the fetus or newborn to the UCLA Data Safety Monitoring Board (DSMB). If a male subject impregnates his female partner the study personnel at the site must be informed immediately and the pregnancy reported to the UCLA DSMB and followed as described above and in Section 7.2.2.

### 5.5.4 Use in Nursing Women

It is unknown whether pembrolizumab is excreted in human milk. Since many drugs are excreted in human milk, and because of the potential for serious adverse reactions in the nursing infant, subjects who are breast-feeding are not eligible for enrollment.

## 5.6 Subject Withdrawal/Discontinuation Criteria

Subjects may withdraw consent at any time for any reason or be dropped from the trial at the discretion of the investigator should any untoward effect occur. In addition, a subject may be withdrawn by the investigator or the UCLA DSMB if enrollment into the trial is inappropriate, the trial plan is violated, or for administrative and/or other safety reasons. Specific details regarding discontinuation or withdrawal are provided in Section 7.1.4 – Other Procedures.

A subject must be discontinued from the trial for any of the following reasons:

- The subject or legal representative (such as a parent or legal guardian) withdraws consent.
- Confirmed radiographic disease progression

*Note:* For unconfirmed radiographic disease progression, please see Section 5.2.2

*Note:* A subject may continue on treatment with confirmed radiographic progression if clinically stable or clinically improved. Unacceptable adverse experiences as described in Section 5.2.1.2

- Unacceptable adverse experiences as described in Section 5.2.1.2
- Intercurrent illness that prevents further administration of treatment

- Investigator's decision to withdraw the subject
- The subject has a confirmed positive serum pregnancy test
- Noncompliance with trial treatment or procedure requirements
- The subject is lost to follow-up
- Completed 24 months of uninterrupted treatment with pembrolizumab or 35 administrations of study medication, whichever is later.

*Note: 24 months of study medication is calculated from the date of first dose. Subjects who stop pembrolizumab after 24 months may be eligible for up to one year of additional study treatment if they progress after stopping study treatment provided they meet the requirements detailed in Section 7.1.5.5*

- Administrative reasons

The End of Treatment and Follow-up visit procedures are listed in Section 6 (Protocol Flow Chart) and Section 7.1.5 (Visit Requirements). After the end of treatment, each subject will be followed for 30 days for adverse event monitoring (serious adverse events will be collected for 90 days after the end of treatment as described in Section 7.2.3.1). Subjects who discontinue for reasons other than progressive disease will have post-treatment follow-up for disease status until disease progression, initiating a non-study cancer treatment, withdrawing consent or becoming lost to follow-up. After documented disease progression each subject will be followed by telephone for overall survival until death, withdrawal of consent, or the end of the study, whichever occurs first.

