### **5.8 Clinical Criteria for Early Trial Termination**

Early trial termination will be the result of the criteria specified below:

1. Quality or quantity of data recording is inaccurate or incomplete
2. Poor adherence to protocol and regulatory requirements
3. Incidence or severity of adverse drug reaction in this or other studies indicates a potential health hazard to subjects
4. Plans to modify or discontinue the development of the study drug

In the event of Merck decision to no longer supply study drug, ample notification will be provided so that appropriate adjustments to subject treatment can be made.

Trial Period:	Screening Phase (Visit 1)	Treatment Cycles a								End of Treatment	Post-Treatment		
		1	2	3	4	To be repeated beyond 8 cycles					Discon	Safety Follow-up Visits b	
Treatment Cycle/Title:						5	6	7	8			3 months post tx	6 months post tx
Scheduling Window (Days):	-28 to -1		± 3	± 3	± 3	± 3	± 3	± 3	± 3	At time of Discon			
Full Physical Examination	X												
Directed Physical Examination		X	X	X	X	X	X	X	X	X	X	X	X
Vital Signs and Weight	X	X	X	X	X	X	X	X	X	X	X	X	X
ECOG Performance Status	X	X	X	X	X	X	X	X	X	X	X	X	X
12-Lead ECG	X												
Laboratory Procedures/Assessments: analysis performed by LOCAL laboratory													
Pregnancy Test – Urine or Serum □-HCG	X												
PT/INR and aPTT	X	X	X	X	X	X	X	X	X	X			
CBC with Differential	X	X	X	X	X	X	X	X	X	X			
Comprehensive Serum Chemistry Panel	X	X	X	X	X	X	X	X	X	X			
Urinalysis	X	X	X	X	X	X	X	X	X	X			
T3, FT4 and TSH	X	X	X	X	X	X	X	X	X	X			
Efficacy Measurements													

Trial Period:	Screening Phase (Visit 1)	Treatment Cycles a								End of Treatment	Post-Treatment		
		1	2	3	4	To be repeated beyond 8 cycles					Discon	Safety Follow-up Visits b	
Treatment Cycle/Title:						5	6	7	8			3 months post tx	6 months post tx
Scheduling Window (Days):	-28 to -1		± 3	± 3	± 3	± 3	± 3	± 3	± 3	At time of Discon			Approx.Q 2 months
Tumor Imaging	X				X			X		X	X	X	X
Brain Imaging	X 												
Tumor Biopsies/Archival Tissue Collection/Correlative Studies Blood													
Archival or Newly Obtained Tissue Collection 	X									X 			
Correlative Studies Blood Collection		X	X	X						X			

1. Brain imaging needed if clinically indicated
2. If patient has not had a biopsy or if tissue is exhausted, patient must undergo a new biopsy for the trial

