## **7.0 TRIAL PROCEDURES**

### **7.1 Trial Procedures**

The Trial Flow Chart - Section 6.0 summarizes the trial procedures to be performed at each visit. Individual trial procedures are described in detail below. It may be necessary to perform these procedures at unscheduled time points if deemed clinically necessary by the investigator.

Furthermore, additional evaluations/testing may be deemed necessary by the UCLA DSMB for reasons related to subject safety. In some cases, such evaluation/testing may be potentially sensitive in nature (e.g., HIV, Hepatitis C, etc.), and thus local regulations may require that additional informed consent be obtained from the subject. In these cases, such evaluations/testing will be performed in accordance with those regulations.

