**Protocol/Amendment No.:**

35

Laboratory tests for hematology, chemistry, urinalysis, and others are specified in Table 5.

Table 5 Laboratory Tests

Hematology	Chemistry	Urinalysis	Other
Hematocrit	Albumin	Blood	Serum $\beta$ -human chorionic gonadotropin†
Hemoglobin	Alkaline phosphatase	Glucose	( $\beta$ -hCG)†
Platelet count	Alanine aminotransferase (ALT)	Protein	PT (INR)
WBC (total and differential)	Aspartate aminotransferase (AST)	Specific gravity	aPTT
Red Blood Cell Count	Lactate dehydrogenase (LDH)	Microscopic exam ( If abnormal )	Total triiodothyronine (T3)
Absolute Neutrophil Count	Carbon Dioxide ‡	results are noted	Free thyroxine (T4)
Absolute Lymphocyte Count	( CO2 or bicarbonate )	Urine pregnancy test †	Thyroid stimulating hormone (TSH)
	Uric Acid		
	Calcium		
	Chloride		Blood for correlative studies
	Glucose		
	Phosphorus		
	Potassium		
	Sodium		
	Magnesium		
	Total Bilirubin		
	Direct Bilirubin ( If total bilirubin is elevated above the upper limit of normal )		
	Total protein		
	Blood Urea Nitrogen		

Hematology	Chemistry	Urinalysis	Other

† Perform on women of childbearing potential only. If urine pregnancy results cannot be confirmed as negative, a serum pregnancy test will be required.
 
‡ If considered standard of care in your region.
			

Laboratory tests for screening or entry into the Second Course Phase should be performed within 10 days prior to the first dose of treatment. After Cycle 1, pre-dose laboratory procedures can be conducted up to 72 hours prior to dosing. Results from the C1D1 tests and C1D1 of Second Course Phase are for information only and do not need to be checked prior to therapy. Other results must be reviewed by the investigator or qualified designee and found to be acceptable prior to each dose of trial treatment.

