##### **7.1.5.1 Screening**

###### **7.1.5.1.1 Screening Period**

Approximately 28 days prior to start of treatment, potential subjects will be evaluated to determine that they fulfill the entry requirements. Screening procedures may be repeated after consultation with the UCLA DSMB.

Written consent must be obtained prior to performing any protocol specific procedure. Results of a test performed prior to the subject signing consent as part of routine clinical management are acceptable in lieu of a screening test if performed within the specified time frame. Screening procedures are to be completed within 28 days prior to the first dose of trial treatment except for the following:

- Laboratory tests are to be performed within 10 days prior to the first dose of trial treatment.
- For women of reproductive potential, a urine pregnancy test will be performed within 72 hours prior to first dose of trial treatment. If urine pregnancy results cannot be confirmed as negative, a serum pregnancy test, performed by the local study site laboratory, will be required.
- Tumor imaging must be performed within 30 days prior to the first dose of trial treatment.

Subjects may be rescreened after initially failing to meet the inclusion/exclusion criteria. Results from assessments performed during the initial screening period are acceptable in lieu of a repeating a screening test if performed within the specified time frame and the results meet the inclusion/exclusion criteria.

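### The only clearly scheduled pregnancy test is before dose 1, so the mandatory pregnancy stop has no routine check behind it during dosing, and testing at Second Course entry is ambiguous

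*Combined protocol and SAP*

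**What the plan says.** Two provisions make pregnancy a stop. Section 5.6 lists, among the reasons a subject must be discontinued, "The subject has a confirmed positive serum pregnancy test". Section 5.5.3 adds: "If a subject inadvertently becomes pregnant while on treatment with pembrolizumab, the subject will immediately be removed from the study".

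One test is clearly scheduled. For women of reproductive potential, Section 7.1.5.1.1 says that "a urine pregnancy test will be performed within 72 hours prior to first dose of trial treatment". The flow chart (Section 6.0) has a separate row, "Pregnancy Test – Urine or Serum", with one mark, under Screening. Coagulation, CBC, chemistry, urinalysis and thyroid tests are marked at Screening, every cycle and discontinuation.

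Other controls exist. Section 5.5.2 requires two contraceptive methods unless the woman is highly unlikely to conceive, and bars entry in doubtful cases ("If there is any question that a subject will not reliably comply with the requirements for contraception"). Section 7.1 says of the trial procedures: "It may be necessary to perform these procedures at unscheduled time points if deemed clinically necessary by the investigator". Section 7.2.2 has investigators report pregnancies that come to them spontaneously.

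For the Second Course, Section 7.1.3 states: "Laboratory tests for screening or entry into the Second Course Phase should be performed within 10 days prior to the first dose of treatment". Table 5 in that section lists urine and serum pregnancy tests, with the note "Perform on women of childbearing potential only". Section 5.6.1 makes re-entry after a complete response conditional on the safety parameters among the eligibility criteria. Section 7.1.5.5 waives re-screening and names no test. Section 7.1.3 also says that Second Course C1D1 results are informational and need no check before therapy.

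**The concern.** The Section 5.6 stop is triggered by a test result, but no routine test after dose 1 is clearly scheduled to produce one. A site following the chart can give dose 2 and every later dose to a woman of childbearing potential without repeating the test. The stop then works only once she or the investigator suspects a pregnancy, and dosing can continue until then. Section 5.5.2 itself recognises possible harm to a fetus. At stake is continued dosing in an unrecognised pregnancy. The response-rate analysis and its power are not touched.

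**Working it through.** The plan gives no figure of its own here, so the check is a reading of the schedule followed by a count of doses.

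**Is a repeat test scheduled in the first course?**
- The chart's pregnancy row is marked at Screening only, and Section 7.1.5.1.1 ties the test to the first dose.
- Table 5 puts the urine pregnancy test in its Urinalysis column, and the chart marks urinalysis at every cycle. Read together, these could imply a test each cycle.
- Table 5's columns do not set timing, however. Its Other column holds coagulation and thyroid tests, which the chart marks at every cycle, together with correlative blood, which the chart marks only at cycles 1 to 3 and discontinuation. A separate row marked at Screening only is therefore the more natural guide.

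Scheduled tests after dose 1, on that reading: 0.

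**Is a test required at Second Course entry?**
- For: Section 7.1.3 asks for laboratory tests within 10 days before the first dose, and Table 5 includes pregnancy tests. On the complete-response route, Section 5.6.1 brings in the eligibility safety parameters, and inclusion criterion 11 requires a negative pregnancy test.
- Against: Section 7.1.5.5 waives re-screening. The 24-month route in Section 5.6 points only to Section 7.1.5.5, which names no test. If a test were treated as a C1D1 laboratory test, Section 7.1.3 would let dosing go ahead before the result was seen.

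Entry testing is therefore ambiguous. No visible text clearly schedules a test in later Second Course cycles.

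**Doses with no scheduled check behind them, per woman of childbearing potential**

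Inputs: one dose every 21 days (Section 5.2); a limit of 35 doses or 24 months, whichever is later (Section 5.6); a 6-month average treatment length (Section 1.0); up to one year of Second Course (Section 7.1.5.5). With uninterrupted dosing, doses in D days = floor(D/21) + 1, and unchecked doses = doses − 1 where a test precedes the first.

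| Period | D (days) | Doses | Unchecked |
|---|---|---|---|
| 35-dose limit | 34 × 21 = 714 | 35 | 34 |
| 24 months | 24 × 30.4375 = 730.5 | floor(34.79) + 1 = 35 | 34 |
| 6-month average | 6 × 30.4375 = 182.6 | floor(8.70) + 1 = 9 | 8 |
| One-year Second Course | 365 | floor(17.38) + 1 = 18 | 17 if an entry test is read in, 18 if not |

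From dose 1 to dose 35 is 714 days, or 102 weeks. The documents give no figure for how long a pregnancy goes unrecognised. At 21-day spacing, each three weeks of delay corresponds to about one further dose.

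**The case against.** The strongest reply is that the plan already controls this risk. It requires a negative baseline test, contraception or abstinence to 120 days after the last dose, no entry where compliance is doubtful, exclusion of those expecting to conceive, an examination at each cycle, unscheduled testing and immediate removal. On that view, adding a routine test is a preference. The controls are real, and it would be wrong to infer that the plan leaves pregnancy unmanaged. None of them, however, detects a pregnancy that nobody suspects.

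The Table 5 column reading also has some textual support. If the sponsor meant it, testing each cycle is already intended and only the chart needs correcting. The chart is in addition incomplete in the text available here: its opening rows and the wording of footnotes a and b, on the treatment-cycle and safety follow-up headers, cannot be seen. The finding assumes that they add no pregnancy test.

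Two points about size stand in full. A reader might take 34 of 35 as exposed doses; it is a maximum-duration count of doses without a scheduled check, and says nothing about how often pregnancy occurs. A reader might also infer that testing before each dose would prevent fetal exposure. It would not. Section 4.2.2 reports a long half-life and target engagement beyond 21 days, so drug from earlier doses is already present at conception. A test taken up to 3 days early can also miss a pregnancy: if the date of turning positive is assumed uniform over a 21-day cycle, up to 3/21 = 14% would turn positive between test and dose.

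**Conclusion.** The point holds as a minor patient-safety gap with a cheap remedy. In the visible plan, the mandatory stop has no clearly scheduled check after dose 1: up to 34 of 35 first-course doses, or 8 of 9 at average duration, are unchecked. It would go too far to say that the Second Course has no entry test; the text supports ambiguity, made worse by the rule that C1D1 results need not be checked. The conclusion rests on the separate chart row prevailing over Table 5's column layout, and on the unseen footnotes adding no test. The number of women of childbearing potential among about 25 subjects is not given and may be small or zero. The efficacy conclusions are unaffected.

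**What to change.** - **Flow chart:** mark the pregnancy row at each cycle from cycle 2, including Second Course cycles, and at discontinuation. Use a urine test run on the sample already taken for urinalysis, within the 72-hour pre-dose window of Section 7.1.3, with the result reviewed before the dose. Confirm by serum test if the result is positive or unclear.
- **Who is tested:** women neither surgically sterilized nor postmenopausal, as Section 5.5.2 defines those terms. Inclusion criterion 12 should not be used for this, because its description of non-childbearing potential fits a woman who can conceive. Section 5.5.2 also counts women who are not heterosexually active as highly unlikely to conceive. The rule above would test them too; the sponsor may exempt them if it says so.
- **Section 7.1.5.5:** require a negative pregnancy test, reviewed before the first Second Course dose, on both the complete-response and 24-month routes. State that for this test it overrides the sentence in Section 7.1.3 making Second Course C1D1 results informational.

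The cost is a chart amendment, the added wording in Section 7.1.5.5 and one extra urine test per cycle in the women concerned. No extra visit is scheduled, but an occasional serum sample and a short dose delay are to be expected.
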